Study coordinators at infusion centres will be responsible for identifying and recruiting patients as they are scheduled or come to the site for their MabThera infusion. For the patient survey, patients meeting the eligibility criteria who visit the participating infusion centres during the data collection period will be given the opportunity to participate in the patient survey until the infusion centre recruitment goal is met. Sites will keep a simple log with information on the number of patients approached about the survey and reasons for refusal for those who refuse to participate. Sites will also keep a log of all eligible patients from whom consent is requested whether they participate or not to the study, and reason for refusal for those who refuse to give consent. The logs will also include minimal information such as age, sex, and clinical indication for MabThera depending on country data privacy policies. The logs will not include any patient identifier and will be kept separate for the survey and medical record abstraction components.

Infusion Centre Recruitment

Approval from each relevant IRB/independent EC will be obtained prior to study start in each country and documented in a letter to the centre specifying the date on which the IRB/EC met and granted approval. Centres will be contacted to confirm their eligibility, assess their interest in participating in the study, and assess the feasibility of implementing data collection.

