Approximately 10-15 infusion centres in each country will be recruited to participate in this study. As part of the feasibility evaluation, Roche provided lists of infusion centres for potential participation. If the target number of participating infusion centres is not achieved, national study coordinators may be required to update and supplement the site lists. The final infusion centres recruited are not intended to reflect a random sample of all infusion centres for biologic treatments in the target countries but rather a generally representative sample of centres administering MabThera. Several factors will be evaluated to ensure a diverse representation of sites, including geographic location, infusion centre type (e.g., outpatient clinic or hospital-based infusion centre), medical specialty of physicians treating the patients (e.g., rheumatology vs. internal medicine), research experience (e.g., academic centre vs. community health centre), and casuistic purpose (e.g., centres that treat mainly off-labels patients vs. centres that treat mainly patients with RA). In addition, during site recruitment, data on site characteristics that may influence patients and their knowledge of the PAC will be collected (e.g., whether or not the PAC is being distributed at the infusion centre and counselling practices at the centre).

Following study start, information will be collected about the distribution or not of the MabThera PAC within each centre. For those infusion centres that are unable to participate or are not interested in participating, reasons for their refusal to participate in the study will be documented as part of the recruitment process.

Patient Selection and Recruitment

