As patients come in for their MabThera infusions or shortly before the visit, the study coordinator at each site will confirm whether selected patients meet eligibility criteria for the study as specified in the study protocol. According to the eligibility criteria, a patient may be invited to participate in either the medical record abstraction component of the study, or both the medical record abstraction and survey components of the study; patients eligible for the latter may choose to participate in either or both components of the study. The study coordinator will present eligible patients with information about the study using a patient recruitment card and instructions. The study coordinator will invite interested and eligible patients to participate in the study, describe the nature of their participation, and obtain informed consent from patients willing to participate.

It is estimated that 20-30 patients will participate to the medical record abstraction in order to yield between 1000-1500 medical records in the DUS. For the patient survey, it is estimated that each infusion centre will recruit 10-14 patients, with the goal of 500-700 patients (approximately 100 patients per country) completing the survey. The estimates are based upon the anticipated number of eligible patients for participation identified in the feasibility evaluation and an adequate level of precision for the estimates (see Section 8.6). This final number of study participants depends on the actual number of patients filling a prescription within the established time frame and on actual response rates for the study.

For centres with a large volume of patients that will most likely reach the maximum number of patients, a patient sampling methodology will be considered to select the specific patients that will participate in the study. The sampling methodology will be designed with the goal of maximising the probability that each patient treated with MabThera will have an equal opportunity to be selected. In some sites, it is likely that all treated patients will be selected. The sampling approach for those sites with larger numbers of patients will be customised for the site (based on patient volume) and will be devised to achieve an efficient method of obtaining a representative patient sample in centres with varying patient administration systems. The sites will be asked to recruit patients for the study when the patients are at the physician practice for a scheduled visit.

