8.5 STUDY SIZE

The results from the feasibility evaluation showed that some large centres recruited more than 100 patients. To avoid large centres being overrepresented in the study population, it is planned to put a cap of 30 patients as the maximum number of patients that a single centre can recruit for either the medical record abstraction component or survey component of the study. To compensate for the 30-patient cap, the recommendation in the feasibility evaluation was to recruit 10-15 infusion centres per country in order to accomplish the recruitment targets for both components of the study.

Medical Record Abstraction Component Study Size

From the estimates obtained in the feasibility evaluation, the Sponsor projects that 20-30 patients per infusion centre will be recruited for the medical record abstraction component of the study, yielding a total of between 1,000 and 1,500 medical records collected during the 10-month period. Because the sample size for the medical record abstraction component of the study will be larger than that for the survey component, there will be greater precision around the estimates of MabThera use by whether the disease indication (RA, SLE/LN, other) represents on-label or off-label use. For example, with a sample of 1,500 patients, if 75% those abstracted are identified as on-label use, then the 2-sided 95% confidence interval (CI) will be 72.8% to 77.2%.

Survey Component Study Size

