8.6 DATA ANALYSIS

Analysis of MabThera off-label use and evaluation of PAC knowledge and utilisation will be descriptive in nature and will entail the tabular display of summary statistics and the frequency distribution of item responses.

A detailed analysis plan describing methods of analysis and presentation, as well as table shells, will be developed prior to starting analysis of data. In addition to describing the analysis of off-label use, for the questionnaire data, the analysis plan will describe any planned comparisons of participants and non-participants. The analysis plan will also describe the following:

- Analysis of subgroups
- · Methods for handling missing data
- Level of statistical precision

All analyses will be performed using SAS 9.2 (or higher) statistical software (SAS Institute Inc., Cary, North Carolina, USA). Programs, logs, and output will be reviewed for accuracy according to relevant standard operating procedures.

The analysis of off-label use will be descriptive and will present MabThera utilisation by indication (RA, SLE/LN, other). Results will be evaluated by site characteristics, including country and geographic region within country, to ascertain any patterns of prescribing by specific indication. The main analysis will be to estimate (with 95% CIs)

^a With an average cluster size of 8 patients, correlation coefficients of 0.15 and 0.30 correspond with design effects of 2.05 and 3.1, respectively.

^b The percentage in this column does not need to represent only the percentage of correct responses; it can represent any percentage, for example percentage of abstractions that were identified as off-label use or percentage of abstractions that had systemic lupus erythematosus (SLE).

the proportion of off-label use among users of MabThera during the entire study period in the 5 European countries of interest. The proportion of each of the most common off-label use indications will be described among the entire off-label use group. In addition, an estimate of off-label usage will be determined amongst prevalent (i.e., repeat infusions) and incident (i.e., patients attending for their first MabThera infusion) patients to the extent that incident use can be accurately determined. Characteristics of patients meeting the definitions for both strict and broad on-label use will also be evaluated. The dosage of MabThera used by infusion will also be estimated in the on- and off-label groups.

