8.9 LIMITATIONS OF THE RESEARCH METHOD

Selection bias is a distortion of evidence or data that arises from the method of collecting samples and data, in other words, resulting from the method by which study patients are selected. The selection bias may undermine the external validity (generalizability) of the study data and results. In this study, a selection bias may arise from:

- The method study sites are selected
- 2. The method patients at the individual sites are selected.

In order to minimize selection bias, the following site and patient selection methods are used. Ten (10) to 15 infusion centres in the participating European countries, preferably from diverse geographical regions within a country, that have prescribed MabThera to patients with non-oncology conditions during the (country-specific) eligibility period will be chosen (see also Section 8.2). A list of potential sites will be reviewed, and in situations where the number of identified sites is greater than the number required for the study, the selection of sites will be randomized. The process of site selection will be carefully documented.

Possible selection bias occurring at the patient level will be minimized by the following selection methods (see also Section 8.2):

- If a site had administered MabThera during the country-specific observation period to not more than 30 (eligible) patients, all these patients will be included in the study.
- If a site had prescribed MabThera during the (country-specific) observation period to more than 30 (eligible) patients, 30 (eligible) patients will be randomly selected from this site to avoid any potential clustering or period effect.

As is the case with all voluntary surveys, invited patients will self-select into the study, and volunteer bias may lead to an underestimate or overestimate of the level of patient awareness.

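### The 30-patient cap ties selection chance to centre size, yet the protocol states no weight and does not require the eligible counts a weight would need; its patient-selection rules also disagree

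*Protocol*

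**What the plan says.** **The cap.** Protocol section 8.5 reports that in the feasibility evaluation "some large centres recruited more than 100 patients". To keep such centres from being overrepresented, "it is planned to put a cap of 30 patients as the maximum number of patients that a single centre can recruit", for the record abstraction or for the survey.

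**Selection at the centre.** Section 8.9 includes every patient at a site with no more than 30 eligible patients. Above that number, "30 (eligible) patients will be randomly selected from this site". Section 8.2 is less definite. For high-volume centres a sampling method is only to be considered, with the goal of "maximising the probability that each patient treated with MabThera will have an equal opportunity to be selected". For the survey, section 8.2 says that eligible attenders are "given the opportunity to participate in the patient survey until the infusion centre recruitment goal is met"; the expected number is 10-14 per centre.

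**The target.** Section 8.6 defines the main analysis as the estimate, with a 95% confidence interval, of "the proportion of off-label use among users of MabThera during the entire study period in the 5 European countries of interest". Detailed methods are left to a later analysis plan. Results are also to be examined by site characteristics. Country and region are named; centre size is not.

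**The centres.** Section 8.2 says they are not a random sample. Among the features used to obtain a diverse mix it lists "casuistic purpose (e.g., centres that treat mainly off-labels patients vs. centres that treat mainly patients with RA".

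**The concern.** The target is a proportion of patients, so each user should count equally. Under the cap a small centre contributes all its eligible patients and a 100-patient centre contributes 30. For a patient-level proportion, including large centres in line with their volume is not overrepresentation; the cap makes them underrepresented. That is harmless only if off-label use does not depend on centre size, or if the analysis restores the balance.

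The protocol itself expects centres to differ in their off-label share, so a link with size is plausible, although it is not documented.

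The correction also needs data that must be planned for. A weight requires each centre's total of eligible patients. Section 8.2 asks for a threshold (at least 20 in the past 12 months) and for logs of patients approached or asked for consent. At a centre above the cap, patients who are not selected need not be asked, so the logs need not show the total. If it is not kept, an analysis plan written later may be unable to use it.

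A second, separate matter is that the passages on how patients are chosen cannot all be followed as written.

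**Working it through.** **1. The plan's own precision figure.** For 75% and n = 1,500 without clustering: 0.75 ± 1.96 × √(0.75 × 0.25 / 1,500) = 0.75 ± 0.022, or 72.8% to 77.2%, as section 8.5 states. With 8 patients per cluster and an intra-class correlation of 0.3, the design effect is 1 + 7 × 0.3 = 3.1 and the half-width is 3.9 points (71.1% to 78.9%), as in Table 1. These are sampling errors only.

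**2. Selection chance before consent**, min(1, 30/N), from sections 8.5 and 8.9: 1 for N up to 30; 0.60 at 50; 0.50 at 60; 0.30 at 100; 0.20 at 150.

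**3. Bias of an unweighted pooled proportion.** Take two kinds of centre, small and large. Let S be the large centres' share of all eligible patients, s their share of included patients, and p the off-label rate. Then bias = (s − S) × (p_large − p_small).

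The documents give no off-label rates by centre size, so all rates and centre mixes here are assumptions. Small centres have 20 patients.

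Worked case, 40 small centres and 10 of size 100, rates 20% and 50%:
- All eligible patients: (800 × 0.20 + 1,000 × 0.50) / 1,800 = 36.7%.
- Capped, unweighted: (800 × 0.20 + 300 × 0.50) / 1,100 = 28.2%, a bias of −8.5 points.
- With 35% at large centres: 28.3% against 24.1%, −4.2 points.
- Weighted by N/n (1 and 100/30 = 3.33): 36.7%, so the patient-level value is recovered.
- Kish variance inflation, n Σw² / (Σw)² = 1,100 × (800 + 300 × 11.11) / 1,800² = 1.40.

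Other mixes, by the same formulas:

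| Small : large (size of large) | Mean size | S | s | Bias at +10 / +20 / +30 points | Kish |
|---|---|---|---|---|---|
| 45 : 5 (60) | 24 | 0.250 | 0.143 | −1.1 / −2.1 / −3.2 | 1.09 |
| 95 : 5 (100) | 24 | 0.208 | 0.073 | −1.4 / −2.7 / −4.1 | 1.27 |
| 45 : 5 (100) | 28 | 0.357 | 0.143 | −2.1 / −4.3 / −6.4 | 1.38 |
| 40 : 10 (100) | 36 | 0.556 | 0.273 | −2.8 / −5.7 / −8.5 | 1.40 |
| 30 : 20 (100) | 52 | 0.769 | 0.500 | −2.7 / −5.4 / −8.1 | 1.29 |

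The signs reverse if large centres have the lower rate. The bias is zero if the rates are equal.

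**4. The selection rules side by side.**
- Section 8.9: all patients, or a random 30, enter the study. No component is named.
- Section 8.2, patient selection: sampling at large centres is to be considered, and patients are enrolled as they attend.
- Section 8.2, survey: attenders are offered the survey until the centre's goal is reached. With a goal of 10-14 and a minimum centre size of 20, this limit may bind even at centres where section 8.9 would take everyone.

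**The case against.** The case on the other side has real force.

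- **Weighting may still come.** A reader might infer that an unweighted analysis is planned. The protocol is only silent; it defers methods to an analysis plan that is not at hand, and weights are commonly fixed there. This stands. What remains is that the count a weight needs is a data-collection matter, and no section requires it. Applying section 8.9 does imply that a site knows whether it exceeds 30, so the count should be easy to obtain, but nothing says it is kept or reported.
- **Equal opportunity.** A reader might infer that the cap contradicts the goal in section 8.2. That sentence introduces the sampling method for centres expected to reach the maximum, so it can be read as an equal chance within a capped centre. A random 30 would meet that. The unequal chance between centres is a fact of the design, but not a clear contradiction of this sentence.
- **The survey quota.** A reader might infer that quota filling biases the off-label estimate. It does not: that estimate comes from record abstraction. The quota bears on the survey results, and that early or frequent attenders would fill it is an inference.
- **Choice of sites.** The purposive mix is disclosed in sections 8.2 and 8.9, and section 8.9 randomises sites when there are more than needed. It is not a hidden defect. It does limit what the pooled figure can represent.
- **Size.** The largest bias above rests on mean centre sizes of 36 or more, against 23-24 in section 8.5. At a mean of 24 the tabulated range is 1.1 to 4.1 points. The 20-patient minimum could raise the mean among admitted centres, so neither figure is firm. The 2.2-point half-width also assumes 1,500 records and no clustering; at an intra-class correlation of 0.3 it is 3.9.

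**Conclusion.** The point holds in conditional form. The cap and section 8.9 fix a selection chance that depends on centre size. The main estimate is a patient-level proportion, no weight is stated, and the eligible count per centre is not required. If the pooled proportion is left unweighted and off-label use varies with centre size, it is biased for users at the participating centres.

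Across the assumed centre mixes, rate differences of 10 to 30 points give a bias of about 1 to 8.5 points in either direction. The upper end exceeds both the 2.2-point and the 3.9-point half-widths; the lower end exceeds neither. With equal rates there is no bias. It would be tempting to conclude that off-label use will be underestimated because it concentrates in large specialist centres; no section says so.

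The mismatch between sections 8.2 and 8.9 on how patients are chosen stands on its own and needs no assumption. Because the centres are not a random sample, even a weighted figure describes the participating centres and not the five countries.

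**What to change.** 1. Require each centre to record its number of eligible patients, for the 12-month look-back (record abstraction) and for the survey window.
2. Report the off-label proportion weighted by eligible over included patients per centre, with centre as the cluster, alongside the unweighted figure. This treats patients who decline consent as similar to participants in the same centre; say so.
3. Reconcile sections 8.2 and 8.9 so that one rule applies to each component, with random order wherever a cap or quota binds. State which component section 8.9 refers to.
4. In section 8.6, describe the pooled figure as applying to the participating centres, not as a five-country rate.

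The cost is one count per centre and component, random ordering at centres that reach a limit, and survey-type procedures in the analysis. The statistical price is a variance inflation of about 1.1 to 1.4 in the mixes examined. Weighting does not repair non-random choice of centres.

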8.1.2 Number of Patients Observed in the Study

Based on the results of a feasibility evaluation, it is estimated that 1,000-1,500 medical records (200-300 per country) of patients receiving MabThera will be abstracted and 500-700 patients (approximately 100 per country) will complete the questionnaire at participating infusion centres.

8.1.3 Centres

This study will be conducted at approximately 10-15 centres in approximately 5 countries, in order to recruit the estimated number of patients for medical record abstraction and survey participation, as described in Section 8.1.2. Additional countries and centres may be added or substituted if underperforming.

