Considering the estimates of the volume of patients available that were provided by the feasibility evaluation, during a 10-month period, a maximum of 720 patients could be recruited for the survey component in the 5 countries, assuming a mean (median) of 23-24 (13-18) patients per centre and 30 participating centres. However, the mean is based on some large centres recruiting more than 100 patients. To avoid large centres being overrepresented in the study population, it is planned to put a cap of 30 patients as the maximum number of patients that a single centre can recruit. The final study size has been set at 500 completed surveys across all countries, with an estimated 10-14 patients recruited per infusion centre for the survey; this will allow reasonable precision around estimates of patient knowledge and understanding of the PAC at the study level. Since it is planned to recruit up to 10-14 patients per infusion centre for the survey, the responses from patients within the infusion centre may be correlated. Assuming no correlation and the percentage of correct responses to a question (or the percentage with off-label use) is 75%, then for a sample of size 500, the 2-sided 95 CI will be 71.2% to 78.8%; whereas the corresponding CI will be 68.3% to 81.7% if there are on average 8 patients per infusion centre with an intra-class correlation of 0.3. A correct response rate of 50% yields the widest possible CI and thus the least precision; the farther the percentage is from 50%, the greater the precision. Table 1 shows 95% confidence limits assuming various combinations of sample size, percentage with correct response, and intra-class correlation coefficients.

Table 1 Confidence Limits for Various Combinations of Sample Size and Correct

Response Percentage

Patient Sample Size	Intra-class Correlation Coefficient ^a	Correct Response ^b (%)	Lower 95% Confidence Limit (%)	Upper 95% Confidence Limit (%)
100	0	25	16.5	33.5
100	0	50	40.2	59.8
100	0	75	66.5	83.5
100	0	90	84.1	95.9
100	0.15	25	12.8	37.2
100	0.15	50	36.0	64.0
100	0.15	75	62.8	87.2
100	0.15	90	81.6	98.4
100	0.3	25	10.1	39.9
100	0.3	50	32.7	67.3
100	0.3	75	60.1	89.9
100	0.3	90	79.6	100.0
500	0	25	21.2	28.8
500	0	50	45.6	54.4
500	0	75	71.2	78.8
500	0	90	87.4	92.6
500	0.15	25	19.6	30.4
500	0.15	50	43.7	56.3
500	0.15	75	69.6	80.4
500	0.15	90	86.2	93.8
500	0.3	25	18.3	31.7
500	0.3	50	42.3	57.7
500	0.3	75	68.3	81.7
500	0.3	90	85.4	94.6
1500	0	25	22.8	27.2
1500	0	50	47.5	52.5
1500	0	75	72.8	77.2

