1500	0	90	88.5	91.5
1500	0.15	25	21.9	28.1

Patient Sample Size	Intra-class Correlation Coefficient ^a	Correct Response ^b (%)	Lower 95% Confidence Limit (%)	Upper 95% Confidence Limit (%)
1500	0.15	50	46.4	53.6
1500	0.15	75	71.9	78.1
1500	0.15	90	87.8	92.2
1500	0.3	25	21.1	28.9
1500	0.3	50	45.5	54.5
1500	0.3	75	71.1	78.9
1500	0.3	90	87.3	92.7

Note: Table calculations assume an average of 8 patients from each practice (cluster).

Calculations performed using SISA software, prevalence module. Uitenbroek DG. Binomial. SISA. 1997. Available at: http://www.quantitativeskills.com/sisa/calculations/preval.htm. Accessed 11 June 2012.

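### Stated precision of the main off-label estimate (±2.2 points) ignores clustering, and Table 1 uses 8 patients per centre where 20-30 are planned; on the protocol's own ICC scenarios it is about ±4 to ±7

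*Protocol*

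**What the plan says.** Section 8.6 makes the main analysis an estimate, with 95% confidence intervals, of "the proportion of off-label use among users of MabThera during the entire study period in the 5 European countries of interest". Section 8.5 gives its precision by example: with 1,500 records, "if 75% those abstracted are identified as on-label use, then the 2-sided 95% confidence interval (CI) will be 72.8% to 77.2" per cent. The same paragraph projects that "20-30 patients per infusion centre will be recruited for the medical record abstraction component of the study", for 1,000 to 1,500 records in all, and says that the larger sample makes this component more precise than the survey. It does not mention correlation within centres.

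Correlation enters only in the survey paragraph, "with an estimated 10-14 patients recruited per infusion centre for the survey", and in Table 1, which uses ICCs of 0, 0.15 and 0.30. Footnote b extends the table to the percentage of abstractions that are off-label. The table note says "Table calculations assume an average of 8 patients from each practice (cluster"), and footnote a gives the resulting design effects as 2.05 and 3.1.

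On the number of centres, Section 8.2 says "Approximately 10-15 infusion centres in each country will be recruited to participate in this study", and Section 8.5 agrees. Section 8.1.3 says "This study will be conducted at approximately 10-15 centres in approximately 5 countries". Section 8.5 caps each centre at 30 patients for either component.

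**The concern.** The design effect grows with the number of patients per centre. The protocol allows for clustering in the text where clusters are small (survey, 10-14) and leaves it out where they are large (records, 20-30). The clustered rows of Table 1 at 1,500 do not repair this, because they describe many more and much smaller centres than the study will have.

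The study answers a regulator's request to quantify off-label use, so a reader will take ±2.2 points as what it can deliver. The expectation that the larger record sample buys markedly better precision also depends on ignoring clustering. Section 8.2 deliberately seeks centres that differ in the outcome itself, some treating mainly off-label patients and others mainly rheumatoid arthritis, so correlation within centres cannot be assumed negligible.

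**Working it through.** **Inputs.** p = 75%; n = 1,000 to 1,500 records; m = 20-30 per centre; ICC = 0.15 and 0.30 (all Section 8.5). Centres: 10-15 per country × 5 = 50-75 (Sections 8.2 and 8.5).

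**Formula.** Half-width = 1.96 × √(p(1−p) × DE / n), with design effect DE = 1 + (m−1) × ICC.

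**Reproducing the protocol.** With n = 1,500 and DE = 1: 1.96 × √(0.1875/1,500) = 2.19 points, so 72.8 to 77.2. The quoted interval is exactly the ICC = 0 case. With m = 8, DE = 1 + 7 × 0.15 = 2.05 and 1 + 7 × 0.30 = 3.1, and the formula returns all 36 rows of Table 1 to the printed decimal. The arithmetic is right; the cluster size is the faulty input.

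**Does m = 8 fit the plan?** 1,500 / 8 = 187.5, about 188 centres, against 50-75 planned.

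**Planned cluster sizes, p = 75%:**

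| n | m | Centres | ICC | DE | Half-width | 95% CI |
|---|---|---|---|---|---|---|
| 1,500 | 30 | 50 | 0.15 | 5.35 | ±5.1 | 69.9-80.1 |
| 1,500 | 30 | 50 | 0.30 | 9.70 | ±6.8 | 68.2-81.8 |
| 1,000 | 20 | 50 | 0.15 | 3.85 | ±5.3 | 69.7-80.3 |
| 1,000 | 20 | 50 | 0.30 | 6.70 | ±6.9 | 68.1-81.9 |
| 1,500 | 20 | 75 | 0.15 | 3.85 | ±4.3 | 70.7-79.3 |
| 1,500 | 20 | 75 | 0.30 | 6.70 | ±5.7 | 69.3-80.7 |

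Table 1 at n = 1,500 shows 71.9-78.1 (±3.1) and 71.1-78.9 (±3.9) for the same two ICCs.

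**Smaller ICCs, n = 1,500, m = 30.** ICC 0.01: DE 1.29, ±2.5. ICC 0.02: DE 1.58, ±2.75. ICC 0.05: DE 2.45, ±3.4. ICC 0.10: DE 3.9, ±4.3.

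**Survey at the planned cluster size.** ICC 0.30, n = 500, m = 10: DE 3.7, ±7.3. ICC 0.30, n = 700, m = 14: DE 4.9, ±7.1. The text states 68.3-81.7, or ±6.7, at m = 8.

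**Gain of records over survey in the same 50 centres.** Survey (n = 500, m = 10): ±5.82 and ±7.30. Records (n = 1,500, m = 30): ±5.07 and ±6.82. The gain is 0.75 points at ICC 0.15 and 0.48 at ICC 0.30. Table 1 suggests 5.4 − 3.1 = 2.3 and 6.7 − 3.9 = 2.8 points.

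**Capacity under Section 8.1.3.** 10-15 centres in all × 30 = 300-450 records. The target of 1,000-1,500 needs the per-country reading: 50 × 20 = 1,000 and 50 × 30 = 1,500.

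**The case against.** The best defence is that no ICC for off-label use is given. The values 0.15 and 0.30 are scenarios introduced for the survey, and with an ICC of 0.02 the interval at n = 1,500, m = 30 is only ±2.75. That stands as a limit on size: ±4 to ±7 is not the true interval. It does not rescue ±2.2, which is too narrow for any positive ICC under this formula. It is also fair that Table 1 discloses clustering at 1,500, though with the wrong cluster size, and that the record component remains somewhat more precise than the survey. For the survey, 8 per centre is not impossible (500 / 8 is about 62 centres), but it disagrees with the stated 10-14.

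A reader might infer more than the documents support:

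- **That reported intervals will cover well below 95%.** This presumes an analysis that ignores centre. Section 8.6 leaves methods and the level of statistical precision to the analysis plan.
- **That the 30 centres in the survey paragraph are a third conflicting count.** That figure belongs to the feasibility volume estimate; Section 8.5 explains the move to 10-15 per country.
- **That Section 8.9 claims to remove within-centre correlation**, because "30 (eligible) patients will be randomly selected from this site to avoid any potential clustering or period effect". Random selection within a site does not remove differences between sites. But the sentence concerns patient-level selection bias, can be read as avoiding patients bunched in time, and makes no statement about variance.
- **That survey precision falls to ±8.4.** That pairs the low total of 500 with the high cluster size of 14, which implies about 36 centres.

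**Conclusion.** The point holds, as a wrong planning input rather than an arithmetic slip. The ±2.2 points quoted for the main estimate assume no clustering, and Table 1's ±3.1 and ±3.9 assume centres far smaller than planned. On the protocol's own ICC scenarios, p = 75% and 50-75 centres, the half-width is about ±4 to ±7. At n = 1,500 in 50 centres that is 2.3 to 3.1 times the quoted figure (5.07/2.19 and 6.82/2.19).

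The size rests on the ICC, which the protocol does not supply for this outcome, and on equal centre sizes; unequal sizes would widen the interval, and stratification by country could narrow it somewhat. Selecting centres for diversity of indication mix makes a sizeable ICC plausible without quantifying it. Nothing here shows that the sample is too small: the study is descriptive, and no hypothesis or precision threshold depends on ±2.2. Section 8.1.3 separately contradicts Sections 8.2 and 8.5 on the number of centres.

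**What to change.** 1. In Section 8.5, restate the record-abstraction interval with its ICC and cluster size, for example the range in the table above, with a line for smaller ICCs.
2. Recompute Table 1 at m = 20 and 30 for n = 1,000 and 1,500, and at the planned 10-14 per centre for the survey. Bring the survey example in the text into line.
3. Qualify the statement that the larger record sample gives greater precision: in the same 50 centres the gain over the survey is about 0.5 to 0.75 points, because the number of centres dominates.
4. Correct Section 8.1.3 to 10-15 centres per country.

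Reported confidence intervals should allow for clustering by centre; that method can sit in the analysis plan. The cost is some wording and one table. The stated precision becomes less favourable, and no extra patients are needed.
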